Research Protocol

The tongue features associated with chronic kidney disease (CKD)

Version 2 , 25-4-2019

Principal Investigator:

Principal Investigator(s): [name]

Institution: CHANGHUA CHRISTIAN HOSPITAL, TAIWAN

CCH IRB No. : 190404

Date of Approval: May 9, 2019

Address: [name]

[contact]

The tongue features associated with chronic kidney disease- study protocol for a randomized crossover trial

I. Study Objectives

The objectives of this protocol are to apply the noninvasive ATDS to evaluate tongue manifestations in patients with CKD, and to provide valuable information for clinical doctors, which can be used to facilitate the early detection and diagnosis of CKD, to analyze the current status of patients, and to dynamically schedule treatment plans. This protocol is a cross-sectional, case-controlled observational study investigating the usefulness of the ATDS in clinical practice by examining its efficacy as a diagnostic tool for CKD.

II. Background and Rationale

Chronic kidney disease (CKD) is an important global public health problem. According to related literatures, the prevalence of CKD is about 11% .(1) CKD is a progressive disease. If it progresses to end-stage renal disease (ESRD), renal replacement therapy: dialysis and renal transplantation, is required to maintain life(2). The growing prevalence and progression of chronic kidney disease (CKD) raises concerns about our capacity to manage its economic burden to patients, caregivers, and society. The societal direct and indirect costs of CKD and end-stage renal disease are substantial and increase throughout disease progression. There is significant variability in the evidence about direct and indirect costs attributable to CKD and end-stage renal disease, with the most complete evidence concentrated on direct health care costs of patients with advanced to end-stage CKD.(2)

CKD, also called chronic kidney failure, is described as a sustained reduction in glomerular filtration rate or evidence of structural or functional kidney abnormalities.(3) Chronic kidney disease (CKD) refers to all five stages of kidney damage, from very mild damage in stage 1 to complete kidney failure in stage 5. CKD symptoms include pain, itch(pruritus), peripheral numbness, sleep disturbances, depression, fatigue, nausea and vomiting. Factors that contribute to these symptoms include anaemia, uraemic toxins, reduced renal capacity, chronic disease-related inflammation, and psychological stress associated with long-term illness.(4)

If it progresses to end-stage renal disease (ESRD), renal replacement therapy, including hemodialysis, peritoneal dialysis and kidney transplantation, is required to maintain life. Therefore, it is essential to find effective and conservative treatment methods to delay the progression of CKD.

Diagnosis in traditional Chinese medicine (TCM) is based on four procedures, observation, smelling or listening, inquiry, and palpation. Tongue diagnosis, serving as a vital non-invasive tool to provide useful clinical information, plays a pivotal role in TCM. The tongue is considered to reflect the physiological and pathological condition of the body, as well as the degree and progression of disease, through the meridians that connect the tongue to the internal organs. By observing tongue features, TCM practitioners can probe qi-blood, yin-yang disorders which are important in treatment selection and prognosis. [18,19] Clinically, practitioners observe tongue characteristics, such as tongue color and shape, fur color and thickness, and the amount of saliva, to help deduce the primary pattern of a patient. However, tongue diagnosis is often biased by subjective judgment, which originates from personal experience, knowledge, diagnostic skills, thinking patterns, and color perception/interpretation. The inconsistency of subjective diagnosis can be improved by using the development of validated instruments. The automatic tongue diagnosis system (ATDS) has shown high consistency and can provide objective and reliable information and analysis of tongue features, facilitating doctors in making effective observations and diagnoses of specific diseases. [10] [18] Previous studies have been conducted on exploring the association between tongue characteristics and specific diseases, including rheumatoid arthritis, [11] breast cancer, [12,13] type 2 diabetes, [14] metabolic syndrome, [15] eczema, [16] dysmenorrhea, [17] and functional dyspepsia, [22] gastroesophageal reflux disease(). However, to the best of our knowledge, no study has yet been performed on the comprehensive scrutiny of tongue features in patients with CKD using ATDS.

III. Procedures

A. Research and Design

Subject Selection/Sample

Inclusion criteria & Exclusion criteria:

All individuals were recruited were informed of the study purpose, procedures, potential risks and benefits, and then the consent form were signed. Subjects will be eligible if they satisfy the following criteria: age over 20 years old; with CKD stage 3-5 including dialysis patients, or who without symptoms and visit clinic for health examination; volunteered to join this research and signed the institutional review board agreement. Both men and women will be enrolled. Subjects with any of the following conditions will be excluded: cancer; acute infection; unable to protrude the tongue stably; risk of temporomandibular joint dislocation

Study setting

The trials will be conducted at the Changhua Christian Hospital. This study will adhere to the recommendations of the Consolidated Standards of Reporting Trials (CONSORT) [15] to allow for greater completeness, transparency and accuracy of reporting. This protocol is a cross-sectional, case-controlled observational study investigating the usefulness of the ATDS in clinical practice by examining its efficacy as a diagnostic tool for CKD stage 3-5 patients. After giving their consent, participants will undergo tongue image capturing using the ATDS. The ATDS examination will be performed under constant environmental conditions and by the same educated operator. The tongue images of both groups: experimental and control groups, were collected by the validated Automatic Tongue Diagnosis System (ATDS) with the corresponding tongue features automatically extracted. We analyzed the data of the subjects and the tongue features from the ATDS.

Eligibility criteria

Information including demography, body mass index (BMI, kg/m²), estimated glomerular filtration rate (eGFR) and CKD Staging were gathered for each subject. The duration of CKD history, comorbidity and complication in experimental group were also collected. Tongue images were collected for each subject to further derive the relevant tongue features of every participant. All personal details and photographs of subjects recruited were encrypted to ensure confidentiality.

Ethics

This research protocol adheres to the principles of the Declaration of Helsinki and has been approved by the institutional review boards of the Changhua Christian Hospital (No. : 190404). Informed consent will be obtained from each participant before any treatment is given. All subjects will have the right to withdraw from the study at any time.

B. Measurement/Instrumentation

Information including demography, body mass index (BMI, kg/m²), estimated glomerular filtration rate (eGFR) and CKD Staging were gathered for each subject. The duration of CKD history, comorbidity and complication in experimental group were also collected. Tongue images were collected for each subject to further derive the relevant tongue features of every participant. All personal details and photographs of subjects recruited were encrypted to ensure confidentiality.

Primary outcome measures. Nine primary tongue features will be extracted from the ATDS as follows: tongue shape: small and thin, moderate, large, and fat; tongue color:

slightly white, slightly red, red, dark red, and dark purple; tooth mark: includes number, average covering area, maximum covering area, minimum covering area, and organs corresponding to the covering area; tongue fissure: amount, average covering area, shortest length, and longest length; fur color: white, yellow, and dye; fur thickness: none, thin, thick; fur amount, average covering area, maximum covering area, minimum covering area, and organs corresponding to the covering area; saliva: includes total area and the amount of saliva (none, little, normal, excessive); ecchymosis: amount, average covering area, maximum covering area, minimum covering area, and organs corresponding to the covering area; red dots: number, average covering area, maximum covering area, minimum covering area, and organs corresponding to the covering area. Feature identification will be further subdivided into 5 segments (spleen–stomach, liver-gall-left, liver-gall-right, kidney, and heart–lung area) according to the theory of traditional Chinese medicine.

Statistical Considerations:

A. Sample Size:

We calculated the sample size will be about 500 with power=0.9, alpha=0.05, effect size convention $r=0.3$, and an anticipated drop-out rate of 10%, using G*Power 3.0.1.0 software which is download from <http://www.gpower.hhu.de>. Every effort will be made to reduce attrition; consent documents will emphasize the importance of complete data and encourage patients to return for the follow-up visit.

B. Randomization:

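### The Objectives offer the tongue system for early detection of CKD, but cases are stage 3-5 and dialysis patients only and no analysis by stage is planned, so detection of stage 1-2 CKD cannot be evaluated

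*Combined protocol and SAP*

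**What the plan says.** Section I (Study Objectives) sets out to describe tongue manifestations in CKD and to supply information "which can be used to facilitate the early detection and diagnosis of CKD". It adds that the study tests the usefulness of the automatic tongue diagnosis system (ATDS) "by examining its efficacy as a diagnostic tool for CKD". Neither statement carries a stage limit.

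Section II (Background and Rationale) says that CKD "refers to all five stages of kidney damage, from very mild damage in stage 1 to complete kidney failure in stage 5".

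Section III.A, under the inclusion and exclusion criteria, admits adults "with CKD stage 3-5 including dialysis patients, or who without symptoms and visit clinic for health examination". The first part of that phrase defines the cases and the second the controls. Study setting, in the same section, repeats the sentence on the tool's purpose but narrows it to "examining its efficacy as a diagnostic tool for CKD stage 3-5 patients".

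Under Eligibility criteria, eGFR and CKD stage are recorded for every subject. For the cases, "The duration of CKD history, comorbidity and complication in experimental group were also collected".

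The Analysis plan (Statistical Considerations, C) names chi-square tests, analysis of variance and logistic regression. It names no analysis by stage, no separate handling of dialysis patients, and no sensitivity, specificity or ROC measure.

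**The concern.** The intended use reaches to the early end of the disease, while the cases come from its middle and late parts. Recording how long each case has had CKD also suggests that these are patients with an established diagnosis.

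With two groups, and no stage-specific analysis, the natural result is a single contrast of all cases with health-check attenders. If many cases are on dialysis, that contrast may be driven by advanced disease. Nothing in the plan would stop it from being read as support for early detection, because the Objectives name that use. What is at stake is the population to which the conclusion applies.

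**Working it through.** **1. Scope, section by section.**

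| Section | CKD stages covered |
|---|---|
| I. Study Objectives | no limit; early detection named as a use |
| II. Background and Rationale | 1 to 5 |
| III.A inclusion criteria (cases) | 3 to 5, including dialysis |
| III.A Study setting (purpose of the tool) | 3 to 5 |
| Statistical Considerations, C | no stage mentioned |

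The Objectives and Study setting disagree. By the protocol's own definition, stages 1 and 2 (two of five) have no cases.

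**2. Does sample size matter?** The only relevant figure in the plan is a total of about 500 (power 0.9, alpha 0.05, r = 0.3, 10% drop-out).
- A two-sided correlation test gives ((1.960 + 1.282)/atanh(0.3))² + 3 = 113, and 113/0.9 = 126 after drop-out. This does not reproduce 500.
- Reading 0.3 as a standardised mean difference gives 468 in total, and 468/0.9 = 520. This is near but not equal.

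The present point does not depend on which is right. Stage 1-2 cases recruited by design are zero for any total.

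**3. What a pooled figure would represent.** The plan gives no stage mix and no stage-specific performance, so every value in this step is assumed. Let w be the share of cases in stage 3, with sensitivity Se3 in stage 3 and SeL in stage 4-5 and dialysis.

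Pooled = w × Se3 + (1 − w) × SeL

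With Se3 = 0.70, SeL = 0.90 and w = 0.50: 0.50 × 0.70 + 0.50 × 0.90 = 0.80.

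Against stage 3, the earliest stage enrolled:
- w = 0.70: pooled 0.76, 6 points above stage 3
- w = 0.50: pooled 0.80, 10 points above
- w = 1/3: pooled 0.833, 13 points above
- Se3 = SeL = 0.80: pooled 0.80 at any w, 0 points

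Against stage 1-2, with pooled 0.80:

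| Assumed sensitivity in stage 1-2 | Pooled minus stage 1-2 |
|---|---|
| 0.30 | +50 points |
| 0.50 | +30 points |
| 0.70 | +10 points |
| 0.80 | 0 |
| 0.85 | −5 points |

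The last two rows need stage 1-2 to be detected better than stage 3, which runs against the Background's view that the tongue mirrors how far a disease has advanced. Within these assumed values, overstatement is the expected direction if that view holds, but the study could not show which row applies.

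**4. Precision of a stage 3 result.** Assume 500 × 0.9 = 450 evaluable subjects, half of them cases (225), and a sensitivity of 0.70. The 95% half-width is 1.96 × √(0.70 × 0.30/n).
- n = 45 in stage 3: 13 points
- n = 75 (one third of cases): 10 points
- n = 112 (about half): 8 points
- n = 225 (all cases, for comparison): 6 points

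**The case against.** The strongest reply is that early detection appears in a subordinate clause, as one intended use among several. The first aim is to describe tongue manifestations in patients with CKD, and stage 3-5 cases serve that at least in part. This stands. The design is not at odds with the whole objective, and a reader who infers that early detection is its sole purpose goes beyond the text.

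The word *early* is not defined. The Background stresses delaying progression to end-stage disease, so non-dialysis stage 3 could be called early relative to that endpoint. This also stands, and is why the point is worded in terms of stage 1-2. It does not rescue the plan, because no stage 3 comparison is specified.

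Study setting already narrows the tool to stage 3-5, and stage is recorded for everyone. That makes the repair easy, but the unlimited wording remains in the Objectives and the Analysis plan remains silent on stage.

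Stage 1-2 subjects might also be present among the symptom-free attenders, since the criteria set no kidney-function rule for that group. They would then be analysed as controls, which gives no estimate of detection in stage 1-2.

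A reader might infer that any pooled detection result must overstate early detection. The documents do not support that. They give no stage mix and no stage-specific performance, they plan no pooled sensitivity, and the gap can be zero or negative under some assumed values. Nor do they state that a pooled contrast will be reported as evidence of early detection.

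**Conclusion.** The point holds in limited form. The Objectives and Study setting contradict each other on scope. By the protocol's five-stage definition no stage 1-2 case is recruited, so detection of stage 1-2 CKD cannot be evaluated. That conclusion rests on the text alone and needs no assumed number.

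A pooled case-control contrast describes only the enrolled stage 3-5 and dialysis mix. That it may overstate performance in earlier disease is conditional on tongue changes growing with severity. The protocol presumes this but does not document it, so no size can be attached. The figures under the working show only how strongly the answer depends on unknown inputs.

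**What to change.** 1. In Study Objectives, limit the diagnostic aim to CKD stage 3-5, matching Study setting. Keep the aim of describing tongue features. Remove early detection from the intended uses and from what the study may conclude.
2. In the Analysis plan, prespecify the case-control comparisons and the logistic model by recorded stage, with dialysis patients as a separate group. Report the number of cases in each stage beside any pooled result, and state that the pooled result applies to that mix.
3. Rest any statement about the earliest stage enrolled only on non-dialysis stage 3 patients against controls, and word it as applying to stage 3.

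No new data are needed, because eGFR and stage are already collected for every subject. The cost is a narrower claim and a less precise estimate in the stage 3 subset: about 10 points of half-width instead of 6 if one third of 225 cases were stage 3 (assumed). A sponsor who wants to keep a claim about stage 1-2 would have to recruit cases in those stages and define the controls' kidney status, which is a larger change.

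### Controls are defined by absence of symptoms, not by kidney status: symptom-free people with CKD can enter the control group, and a symptom-free person with stage 3-5 fits both groups

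*Combined protocol and SAP*

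**What the plan says.** One sentence in section III.A (Inclusion criteria & Exclusion criteria) covers both groups. It admits adults "with CKD stage 3-5 including dialysis patients, or who without symptoms and visit clinic for health examination". The branches are not labelled, but the Study setting text speaks of an experimental and a control group, and the second branch is the only candidate for the controls.

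The exclusions are "cancer; acute infection; unable to protrude the tongue stably; risk of temporomandibular joint dislocation". None concerns kidney function or kidney history.

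Section II (Background and Rationale) describes CKD as "a sustained reduction in glomerular filtration rate or evidence of structural or functional kidney abnormalities" and says that it "refers to all five stages of kidney damage, from very mild damage in stage 1" upwards. Symptoms are not part of that definition. The same section states that "the prevalence of CKD is about 11" per cent.

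Section III.A (Eligibility criteria), repeated in III.B, says that "estimated glomerular filtration rate (eGFR) and CKD Staging were gathered for each subject". Nothing there, or in the Analysis plan, uses these data to form, screen or reassign the groups.

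On the target condition the protocol points two ways. Section I wants to "facilitate the early detection and diagnosis of CKD", with no restriction on stage. The Study setting text names stages 3 to 5 as the target of the diagnostic tool.

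**The concern.** The comparison between CKD patients and controls is the study's only contrast. The chi-square tests, the analysis of variance, the logistic regression and any claim about diagnostic use all depend on who is in each group. Being free of symptoms does not establish being free of CKD as the protocol defines it, so the written rule can place people with CKD in the reference group.

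If their tongues resemble those of the cases, group differences and odds ratios move toward the null, and a correct positive from the tongue system in such a person counts as a false positive. An open assignment rule also leaves room to decide where a person belongs after the tongue features have been seen.

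**Working it through.** **Step 1. Who qualifies for which group, as written**

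| Symptom-free health-check attender | Meets case criterion | Meets control criterion | CKD by section II |
|---|---|---|---|
| No CKD | no | yes | no |
| Stage 1-2 | no | yes | yes |
| Stage 3-5 | yes | yes | yes |

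The last two rows are the defect. It follows from the text and needs no numerical assumption.

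**Step 2. Inputs for the size**

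- Share *p* of controls with CKD: 3%, 5% and 11%. Only 11% is in the protocol, as a general prevalence of CKD. The lower values are assumed.
- Likeness *k* of these controls to cases: *k* = 1 (fully case-like) is the upper bound. *k* = 0 means no dilution.
- Sensitivity 80% and specificity 90%: assumed. The Analysis plan names no accuracy measure; these illustrate the diagnostic aim.
- Feature present in 50% of cases and 30% of true controls: assumed, to illustrate the planned logistic regression.

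**Step 3. Upper bound, *k* = 1**

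- Mean difference: observed = (1 − *p*) × true.
- Specificity: observed = 1 − [(1 − *p*) × 0.10 + *p* × 0.80].
  - *p* = 0.03: 1 − (0.097 + 0.024) = 0.879
  - *p* = 0.05: 1 − (0.095 + 0.040) = 0.865
  - *p* = 0.11: 1 − (0.089 + 0.088) = 0.823
- Odds ratio: the true value is (0.5/0.5) / (0.3/0.7) = 2.33. At *p* = 0.11 the control rate becomes 0.89 × 0.30 + 0.11 × 0.50 = 0.322, and the odds ratio is 1 / (0.322/0.678) = 2.11.

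| *p* | Mean difference shrinks by | Apparent specificity |
|---|---|---|
| 3% | 3% | 88% |
| 5% | 5% | 87% |
| 11% | 11% | 82% |

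**Step 4. Partial likeness**

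In general the mean difference shrinks by *kp* and specificity falls by *kp* × (0.80 − 0.10). With *p* = 0.11 and *k* = 0.5, the difference shrinks by 5.5% and specificity reads 0.90 − 0.055 × 0.70 = 0.8615, about 86%.

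**Step 5. Power**

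The planned total of about 500 does not follow from its stated inputs if 0.3 is a correlation: two-sided, that gives 113 before and 126 after 10% drop-out. It is approached only if 0.3 is read as a standardised mean difference (468 before, 520 after). That mismatch is a separate matter, but it decides what dilution does to power. Assume equal groups and 500 × 0.9 / 2 = 225 evaluable per group; the protocol states no case-to-control ratio.

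- 0.3 as a standardised difference: power is 0.889 without dilution. At 11% the difference is 0.3 × 0.89 = 0.267 and power is 0.808.
- 0.3 as a correlation (standardised difference 2 × 0.3 / √0.91 = 0.629): power stays above 0.99 even with 20% of controls case-like. The harm is then bias in the estimates, not lost power.

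**The case against.** - **Stage 1-2 attenders may be proper controls.** Against the stage 3-5 target in the Study setting text they are true non-cases, and a positive result in them is a real false positive. This stands in part. The aim in section I and the five-stage definition in section II point the other way, so the target is unclear. It is a reason to report these people separately rather than simply drop them: leaving them out removes borderline non-cases and can overstate specificity.
- **The stage 3-5 overlap resolves itself.** Every subject is staged, and stage 3-5 is the case criterion, so the natural reading puts such an attender in the CKD group. That is the sensible reading, but the protocol does not state it.
- **The figures are a ceiling.** This stands. The 11% is a general figure that does not separate the stages, full likeness is assumed, and no accuracy analysis is planned.
- **The gap can be closed at analysis.** True, because stage is recorded for everyone. But unless the rule is fixed before the tongue features are viewed, the choice can depend on the results.

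A reader might infer that the control group is known to contain the disease being detected, so that every feature difference is biased toward zero. The documents do not support that. They give no CKD rate among attenders, stage 1-2 people are arguably non-cases, and dilution affects only features on which the misplaced controls resemble cases. A reader might also expect a numerical eGFR cut-off for controls. The protocol contains none, and the point does not need one.

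**Conclusion.** The point holds as a defect of group definition. As written, the control criterion does not exclude CKD, a symptom-free person with stage 3-5 is eligible for both groups, and a person with stage 1-2 enters as a control despite the five-stage definition and the early-detection aim.

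The effect on results is conditional. At most, under full likeness and an 11% share, differences shrink by 11% and an assumed 90% specificity reads 82%. At 3% it reads 88%, and with partial likeness the loss is smaller in proportion. The true share among health-check attenders and the likeness of their tongues to those of cases are unknown from the documents. Loss of power is a concern only if 0.3 is read as a standardised difference. The repair is nearly free and removes an avoidable source of bias, so it should be made before any tongue features are examined.

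**What to change.** Add to the eligibility criteria, and repeat in the Analysis plan, a rule that forms the groups from the eGFR and CKD stage already gathered for each subject, applied before tongue features are viewed:

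1. Attenders staged 3-5 are analysed in the CKD group and not as controls.
2. The primary control group is attenders with no CKD stage assigned.
3. Attenders staged 1-2 are reported as a separate group, and a sensitivity analysis returns them to the controls. This shows the result for the narrower stage 3-5 target and guards against an overstated specificity.

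State how staging is done for attenders, and say whether the diagnostic target is CKD of any stage or stages 3 to 5.

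**Cost:** a few sentences of text and one extra analysis. A few attenders are reassigned or leave the primary control group. The limit is that the protocol lists no urine test, imaging or repeat eGFR, so stage 1-2 is identified only as well as the existing staging allows, and some such people may remain among the controls.

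### Tooth mark is a primary feature derived for every participant, but teeth and dentures are neither an entry condition nor a listed data item, so unrecorded tooth loss can create or hide a CKD difference in it

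*Combined protocol and SAP*

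**What the plan says.** Section III.B (Measurement/Instrumentation) introduces the primary outcomes with "Nine primary tongue features will be extracted from the ATDS as follows". One of them is "tooth mark: includes number, average covering area, maximum covering area, minimum covering area, and organs corresponding to the covering area". The same section says "Tongue images were collected for each subject to further derive the relevant tongue features of every participant", and gives no category for a feature that cannot be assessed.

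Under Inclusion criteria & Exclusion criteria in III.A, the age condition is "age over 20 years old", with no upper bound. The four exclusions are "cancer; acute infection; unable to protrude the tongue stably; risk of temporomandibular joint dislocation". None concerns teeth.

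On data items, III.A (Eligibility criteria) and III.B both state "Information including demography, body mass index (BMI, kg/m²), estimated glomerular filtration rate (eGFR) and CKD Staging were gathered for each subject". They add, for cases only, "The duration of CKD history, comorbidity and complication in experimental group were also collected". No dental item is listed for either group.

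The cases are patients with CKD stage 3-5, dialysis included. The controls are symptom-free people attending for a health check. No matching is stated. The Analysis plan (Statistical Considerations, C) specifies chi-square tests, analysis of variance and logistic regression, and names no covariate.

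**The concern.** A tooth mark is an imprint of the teeth on the edge of the tongue. In a subject with no teeth in the mouth at imaging it cannot occur, whatever the state of the kidneys. If such a subject is given a count of zero, the value is the same as for a subject with teeth and a smooth tongue edge, and the data set as listed cannot tell the two apart.

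That would matter less if tooth loss were equally common in both groups. Nothing in the design makes it so, because the groups are drawn from different sources without stated matching. More tooth loss among cases would push the comparison towards fewer tooth marks in CKD, or cancel a true excess. More tooth loss among controls would do the reverse. The stated aim is to judge the imaging system as a diagnostic tool for CKD, so a tooth-mark signal that really reflects dentition would mislead that use.

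**Working it through.** The documents give no rate of tooth loss or of tooth marks, so there is no plan figure to reproduce. What follows is an illustration.

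**From the documents.** Total of about 500, drop-out 10%, significance at P<.05 (Statistical Considerations, A and C).

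**Assumed.**
- Equal groups: 500 × 0.9 / 2 = 225 per group.
- A present/absent outcome and a two-sided two-proportion test.
- Edentulous subjects scored zero.
- Prevalence *p* of tooth marks among subjects with teeth, and edentulous share *e*, as shown below.

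**Formulas.**
- Observed prevalence in a group = *p*(1 − *e*).
- With *d* the absolute difference, *m* the mean of the two prevalences and *n* = 225: SE0 = √(2*m*(1 − *m*)/*n*), and SE1 = √((*p1*(1 − *p1*) + *p0*(1 − *p0*))/*n*).
- Chance of P<.05 = Φ((*d* − 1.96 SE0)/SE1) + Φ((−*d* − 1.96 SE0)/SE1).

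**Worked case, 20% v 5% edentulous, *p* = 0.50 in both groups.** Observed 0.50 × 0.80 = 0.400 and 0.50 × 0.95 = 0.475, so *d* = 0.075 and *m* = 0.4375. SE0 = 0.0468 and SE1 = 0.0466. The first term is Φ((0.075 − 0.0917)/0.0466) = Φ(−0.36) = 0.36, and the second is below 0.001. The chance is 36%.

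**No true difference among subjects with teeth.**

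| Edentulous, cases v controls | Observed at *p* = 50% | Odds ratio | Chance of P<.05 | Range for *p* = 30% to 70% |
|---|---|---|---|---|
| 5% v 2% | 47.5% v 49.0% | 0.94 | 6% | 6% to 8% |
| 10% v 3% | 45.0% v 48.5% | 0.87 | 12% | 8% to 19% |
| 20% v 5% | 40.0% v 47.5% | 0.74 | 36% | 19% to 63% |
| 30% v 5% | 35.0% v 47.5% | 0.60 | 77% | 45% to 97% |

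**True difference hidden.** A true 60% v 50% among subjects with teeth (odds ratio 1.5) has a 57% chance of P<.05. At 20% v 5% edentulous it appears as 0.60 × 0.80 = 48.0% v 0.50 × 0.95 = 47.5% (odds ratio 1.02), and the chance is 5%. A true 65% v 50% has 90% power. This falls to 78% at 5% v 2% and 57% at 10% v 3%. At 20% v 5% the chance is 16%.

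**If dentures leave marks.** Suppose 25% of edentulous subjects show marks. The 20% v 5% case becomes 0.50 × 0.80 + 0.25 × 0.20 = 45.0% v 0.50 × 0.95 + 0.25 × 0.05 = 48.75%. The chance of a false P<.05 drops from 36% to about 13%. At 30% v 5% it drops from 77% to about 26%.

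**The case against.** - **The zero score is an inference.** A reader might conclude that the system does score toothless subjects as having no marks. The documents say only that features are extracted automatically and derived for everyone. They do not say what the system returns for such a subject, or whether the operator can flag a feature as not assessable. This stands, and the point is worded as *may be scored*.
- **Dentures may leave marks.** This also stands. It shrinks the illustrated error, and denture status is itself not listed.
- **The effect may be negligible.** At 5% v 2% edentulous the false-positive rate is close to nominal. A reader might infer that tooth loss does differ materially between the groups. The documents contain no figure for that, only different sources and no stated matching.
- **The outcome is listed as number, area and location.** The present/absent test is a simplification, so the percentages indicate scale only. The equal split is likewise assumed.
- **The gap may not be permanent.** A reader might think it cannot be repaired afterwards. A list linking identifiers to names is kept, so subjects could in principle be asked later, although whether dentures were in at imaging would be hard to recover. Age could enter the logistic regression, but no covariate is named, and age accounts for only part of tooth loss. The data list is not plainly exhaustive and the case report form is not shown.
- **Dropping toothless subjects changes the population** to which a diagnostic result applies. This stands, and it is why the all-subject result should also be reported.

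**Conclusion.** The gap is real but conditional. Followed as written, the plan cannot separate a tooth-mark difference due to tooth loss from one due to CKD. It affects one of the nine primary features; the other eight do not depend on teeth in this way. The size cannot be read from the documents. Under the stated assumptions it runs from no material inflation of the false-positive rate (about 6%) to a serious one (77%), and a true difference can be lost. The larger figures need tooth loss to be both common and unequal, with edentulous subjects scored zero. Without a dental item the sponsor cannot show which scenario applies. The documents do not establish that a bias is present, or its direction. The correction is worth making because it is cheap.

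**What to change.** At imaging, record for every subject in both groups whether natural teeth are present, partial or absent, and whether dentures are in or out. In the Analysis plan, state that the tooth-mark feature is analysed in subjects with natural teeth, that absence of natural teeth is coded as not assessable and not as zero, and that partial dentition enters as a covariate. Report the all-subject result beside it, because that is the population for the diagnostic aim. The remaining eight features keep the full sample.

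The cost is one extra item on the case report form, a short addition to the Analysis plan, and slightly fewer subjects for this one feature.
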